3 LIST OF ABBREVIATIONS AND DEFINITION OF TERMS

Abbreviations

AE	adverse event
ALT	alanine aminotransferase
APC	antigen-presenting cell
ASA	aminosalicylic acid
AST	aspartate aminotransferase
BCG	bacille Calmette-Guérin
CD	cluster of differentiation
CFR	Code of Federal Regulations
ECG	electrocardiogram
eCRF	electronic case report form
EDC	electronic data capture
EU	European Union
FAS	full analysis set
FDA	Food and Drug Administration
FSH	follicle-stimulating hormone
GCP	Good Clinical Practice
GLP	Good Laboratory Practice
HEENT	head, eyes, ears, nose, and throat
HIPAA	Health Insurance Portability and Accountability Act
HIV	human immunodeficiency virus
HRQL	health-related quality of life
IBD	inflammatory bowel disease
IBDQ	Inflammatory Bowel Disease Questionnaire
ICF	informed consent form
ICH	International Conference on Harmonisation
IEC	Independent Ethics Committee
IGRA	interferon gamma release assay
IRB	Institutional Review Board
IRT	Interactive Response Technology
IV	intravenous
KKD	Kyowa Kirin Pharmaceutical Development, Inc.
LTE	long-term extension
mAb	monoclonal antibody
MedDRA	Medical Dictionary for Regulatory Activities
mMES	modified Mayo endoscopy subscore
NOAEL	no-observed-adverse-effect level
OECD	Organisation for Economic Co-operation and Development
OLE	open-label extension
PBMC	peripheral blood mononuclear cell
PD	pharmacodynamic(s)
PK	pharmacokinetic(s)
PPD	purified protein derivative

Abbreviations (continued)

SAE	serious adverse event
SAP	statistical analysis plan
SC	subcutaneous
SUSAR	Suspected Unexpected Serious Adverse Reaction
TB	tuberculosis
TEAE	treatment-emergent adverse event
TNF	tumor necrosis factor
TNF- α	tumor necrosis factor-alpha
TNFR	tumor necrosis factor receptor
UC	ulcerative colitis
UCEIS	Ulcerative Colitis Endoscopic Index of Severity
ULN	upper limit of normal
US	United States
WOCBP	women of childbearing potential
wr-CRP	wide-range C-reactive protein

Definitions (Refer to Appendix 1 for Primary and Secondary Efficacy Definitions)

AUC	area under the concentration-time curve
AUC _{0-t}	area under the serum drug concentration-time curve from 0 to the last measurable concentration
AUC _{2wk}	area under the serum drug concentration-time curve at 2 weeks post-dose
AUC _{0-τ}	area under the serum drug concentration-time curve within a dosing interval
AUC _{0-∞}	area under the serum drug concentration-time curve from 0 to infinity
CLs	systemic serum clearance
C _{max}	maximum observed serum concentration
C _{min}	trough concentration at the end of the dosing interval
%CV	percent coefficient of variation
R _{ac}	accumulation ratio
SD	standard deviation
t _{1/2}	terminal elimination half-life
t _{max}	time of maximum observed serum concentration
V _{ss}	volume of distribution at steady state
V _z	volume of distribution at terminal phase

4 BACKGROUND INFORMATION

4.1 Ulcerative Colitis

Inflammatory bowel diseases (IBDs) comprise ulcerative colitis (UC) and Crohn's disease, which are considered to be common gastrointestinal autoimmune diseases, and are referred to as immune-mediated inflammatory diseases. (Mahmood, 2012; Khor, 2011) A peak incidence of UC occurs early in adult life (15 to 30 years) with a greater prevalence in males, nonsmokers or ex-smokers, and in developed countries. (Loftus, 2004; Hanauer, 2006) The global incidence rate of UC varies greatly from 0.5 to 24.5 per 100,000 persons. (Lakatos, 2006)

Urbanization and variances in exposure to sunlight, pollution, and industrial chemicals are considered potential contributing factors to IBD. (Hanauer, 2006) Other factors such as diet, oral contraceptives, perinatal and childhood infections, or atypical mycobacterial infections have been suggested but not proven to play a role. (Loftus, 2004)

Ulcerative colitis symptoms include abdominal pain/cramps, diarrhea that is usually bloody, and severe urgency to have a bowel movement. The symptoms can be intermittent with fairly long periods between flare-ups and remission. Fatigue and loss of appetite with subsequent weight loss are common. Complications can include severe abdominal bloating, bleeding from deep ulcerations, anemia, fulminant colitis, and toxic megacolon potentially leading to perforation of the colon. In addition, there may be skin lesions, joint pain, eye inflammation, and liver disorders. Patients with UC are at increased risk of colon cancer. (Centers for Disease Control and Prevention, IBD, 2015)

Ulcerative colitis is characterized by inflammation limited to the colon that begins in the rectum and affects the superficial layers of the colon in an even and continuous distribution. The inflammatory changes are limited to the mucosa and submucosa with cryptitis and crypt abscesses. Ulcerative colitis is considered to result from an improper mechanism and continuing inflammatory response to commensal microbes and environmental conditions in patients with genetic risk factors. (Khor, 2011) The intestinal mucosa exists in a functional equilibrium with the complex luminal environment dominated by a spectrum of microbial species and their products. A functional balance is essential to maintaining normal mucosal physiology. In addition to nutrient absorption, intestinal epithelial cells perform both barrier and signal-transduction functions. Patients often have a compromised mucosa and an increase in presence of mucolytic bacteria. (Khor, 2011)

Genome-wide association studies have identified 99 non-overlapping genetic risk loci in IBD including 47 risk loci specific to UC of which approximately 30% (28) of IBD-related genetic loci are shared between UC and Crohn's disease. (Franke, 2010; Anderson, 2011) Analyses of the genes and genetic loci that contribute to IBD susceptibility show a multitude of pathways that are critical for intestinal homeostasis, including barrier function, epithelial restitution, microbial defense, innate immune regulation, reactive oxygen species generation, autophagy, regulation of adaptive immunity, endoplasmic reticulum stress, and metabolic pathways associated with cellular homeostasis. Homeostasis in the gut involves a balance between anti-inflammatory and pro-inflammatory signals, whereas an inadequate T-reg-cell response occurs with a heightened response mainly involving Th2 cells in UC. (Khor, 2011)

A recent study showed significantly enhanced apoptosis of circulating lymphocytes in IBD patients during flare-ups compared to remission and is considered to be possibly a consequence of the systemic disease process. (El-Hodhod, 2013) Increased circulating lymphocytes apoptosis may also be attributed to a deficiency in nutrients, which is common in IBD patients. (Bager, 2011; El-Hodhod, 2013; Nakajima, 2011; Levin, 2011; O'Malley, 2011; Yakut, 2010)

Cells with high synthetic capacity and secretory activity (e.g., Paneth and goblet) have high baseline levels of endoplasmic reticulum stress, leading to activation of the unfolded protein response, which controls cellular programs that allow proper protein processing. This response is mainly cytoprotective, although it can signal apoptosis after sustained endoplasmic reticulum stress. (Khor, 2011) The role of apoptosis in intestinal lymphocytes in IBD shows that the inflamed gut T-cells have a resistance to apoptosis, a prolonged survival, and an increased cytokine production that may significantly aggravate the inflammation, whereas noninflamed gut T-cells have an increased susceptibility towards apoptosis that limits expansion of T-cells and down regulates mucosal immune responses. (Sturm, 2008)

In addition to its effects on cell viability and disruption of normal intestinal homeostasis, due to an imbalance of production and apoptosis, sustained endoplasmic reticulum stress also activates autophagy and IL-23 release, and may engage inflammatory circuits that are subsequently propagated by T cells. (Goodall, 2010; Kaser, 2008; Khor, 2011)

Apoptotic cells have been shown to actively suppress inflammatory responses by reducing the lifespan of activated lymphocytes. (Bodar, 2007; El-Hodhod, 2013; Fadok, 2001) Thus, apoptosis plays a critical role in lymphocyte development and homeostasis. Enhanced lymphocyte apoptosis can cause immunodeficiency through cell loss. Conversely, inhibition of apoptosis can lead to the development of autoimmunity or lymphoma. Two major

pathways contribute to the regulation of lymphocyte cell death, death by neglect and death by instruction. (El-Hodhod, 2013; Rathmell, 2002) Increased circulating lymphocyte apoptosis could also be considered as a protective mechanism against organ injury as increased lymphocyte apoptosis was found to be linked to anti-inflammatory cytokine secretion and thereby may contribute to preventing unwanted immune response and organ injury. (El-Hodhod, 2013; Neuman, 2007)

The event that initiates the immune response in IBD has not been identified, but possible factors include a pathogenic and nonpathogenic organism, an immune response to an intraluminal antigen (e.g., protein from cow milk), or an autoimmune process. (Abraham, 2011; El-Hodhod, 2013; Nell, 2010) During an immune response, homeostasis is disturbed as antigen-presenting cells (APCs) become activated and promote the clonal expansion of antigen-specific lymphocytes. Shortly after the peak of the response, controlled induction of apoptosis, of both APCs and lymphocytes, restores homeostasis. This process is critical to ensure protective immunity and avoid lymphoid neoplasia and autoimmunity. (El-Hodhod, 2013; Hildeman, 2007) The influence of tumor necrosis factor (TNF) on the function of APCs varies as TNF can either activate APCs, augment antigen presentation capability, or upregulate the expression of costimulatory molecules, or TNF can inhibit the function of mature lymphocytes and possibly induce their apoptosis and impair antigen presentation to prevent the organ damage. It has been demonstrated that the addition of apoptotic lymphocytes to endotoxin-stimulated peripheral blood mononuclear cells (PBMCs) causes a shift from secretion of proinflammatory cytokines (TNF- α , IL-1 β , and IL-12) to anti-inflammatory cytokines (IL-10). (Voll, 1997)

4.2 Current Treatment of Ulcerative Colitis and Associated Benefit/Risks

Topical or oral 5-aminosalicylic acid (5-ASA) is the first line of treatment for mild to moderately active UC. Patients with persistently active disease are then typically given oral glucocorticoids to induce remission. Once remission is achieved, maintenance therapy, typically with 5-ASA, is recommended for those with left-sided colitis, pancolitis or extensive disease.

Patients with severe UC are usually treated with oral glucocorticoids, high dose oral 5-ASA and topical therapy, and often receive antibiotic treatment as well as nutritional support. Patients with severe or corticosteroid-dependent disease receive additional treatment, such as azathioprine or 6-mercaptopurine, or a biologic agent. Tumor necrosis factor-alpha (TNF- α) blockers are used to treat autoimmune diseases, including Crohn's disease and UC, either

after first-line immunosuppressors (e.g., azathioprine or 6-mercaptopurine) or in association with these treatments. (Silva, 2010)

The following are approved TNF- α blockers:

- Chimeric IgG monoclonal antibody (mAb) infliximab (Remicade; Inflectra and Remsima - in the European Union [EU] only) - UC/Crohn's disease
- Human IgG mAb adalimumab (Humira) - UC/Crohn's disease
- Fully human mAb golimumab (Simponi) - UC
- Pegylated humanized Fab' fragment certolizumab pegol (Cimzia) - Crohn's disease in the United States (US) only

A humanized IgG1 mAb, vedolizumab (Entyvio[®]), which is an integrin receptor antagonist (i.e., binds to the human $\alpha 4\beta 7$ integrin) is approved for both UC and Crohn's disease in the US and EU.

Serious and sometimes fatal adverse effects have been reported with TNF- α blockers (Silva, 2010), including infections due to bacterial, mycobacterial (e.g., tuberculosis [TB]), invasive fungal infections (e.g., histoplasmosis, aspergillosis, candidiasis, coccidiomycosis, blastomycosis, and pneumocystosis), viral (e.g., hepatitis B), or other opportunistic pathogens (e.g., *Listeria* and *Legionella*). (US Food and Drug Administration, Drug Safety Communications, 2011 and 2013) Lymphoma, including a rare and fatal type called hepatosplenic T-cell lymphoma, and other malignancies, can occur in adults and children. Other serious risks include melanoma and Merkel cell carcinoma, heart failure, demyelinating disorders, hypersensitivity reactions, and hepatitis B reactivation. (Marion, 2013)

A review of the subject's prior medical history of neoplasias and infections, and evaluation for active TB and demyelinating diseases, testing for hepatitis B viral infection and latent infection should be conducted. (Silva, 2010)

4.3 KHK4083 - Investigational Product

4.3.1 KHK4083 Development

KHK4083 is a fully human, non-fucosylated IgG1 mAb specific for the costimulatory molecule OX40 (cluster of differentiation [CD]134, tumor necrosis factor receptor [TNFR]SF4), a TNFR family member. KHK4083 binds with high affinity and specificity to an extracellular domain epitope of OX40, which plays a key role in maintaining late T-cell proliferation and survival by suppressing apoptosis, and in inducing T-cell memory formation. OX40 has a unique pattern of expression, being restricted to antigen-activated,

effector T-cells (mostly CD4⁺), transient, and present in diseased areas in human autoimmune diseases.

OX40 has been shown to be highly expressed in the gastrointestinal tissue of patients with autoimmune diseases of the gastrointestinal tract (e.g., celiac, UC, Crohn's disease). In a study on the expression of OX40, all UC and Crohn's disease and most celiac disease biopsy tissue samples (formalin-fixed, paraffin-embedded tissue stained with anti-OX40 antibody and alkaline phosphatase-anti alkaline phosphatase method [APAAP]) were positive, indicating the potential role of OX40 in pathogenesis of these diseases. (Stüber, 2000)

Expression of lymphocyte-endothelial receptor-ligand pairs, $\alpha 4\beta 7$ /MAdCAM-1 and OX40/OX40 ligand in the colon and jejunum of patients with IBD also have been assessed by using endoscopic and per oral jejunal biopsy specimens that were immunostained (i.e., by indirect alkaline phosphatase using antibodies against CD3, ICAM-1, $\alpha 4\beta 7$, MAdCAM-1, and OX40). The expression of MAdCAM-1 and OX40 ligand on gut endothelial and OX40+ cells was increased in sites of mucosal inflammation in patients with IBD. There was no evidence of increased lamina propria T-cells or increased vascular adhesion molecule expression in the proximal intestine of patients with distal IBD. (Souza, 1999)

4.3.2 Nonclinical Development

The generation of the KHK4083 mAb and its *in vitro* characterization as well as the non-clinical pharmacology, pharmacokinetics (PK), and toxicology study reports are thoroughly described in the Investigator's Brochure. All nonclinical safety studies were conducted in Japan, a member country of the Organisation for Economic Co-operation and Development (OECD) and compliant with the Mutual Acceptance of Data program. The studies conducted in accordance with the OECD Test Guidelines and Principles of Good Laboratory Practice (GLP) are identified in the Investigator's Brochure. The nonclinical/toxicological program includes a pivotal 4-week intravenous (IV) GLP study (SBL303-081) and a pivotal 26-week subcutaneous (SC) and IV GLP study (SBL303-104) in cynomolgus monkeys. In these studies, the no-observed-adverse-effect levels (NOAELs) were ≥ 100 mg/kg (IV) and ≥ 30 mg/kg (both SC and IV), in 4-week IV and 26-week SC and IV study, respectively. The mean $AUC_{0-\infty}$ (area under the serum drug concentration-time curve from 0 to infinity) and mean C_{max} for male and female monkeys in the 100 mg/kg dose group were 607000 $\mu\text{g}\cdot\text{hr}/\text{mL}$ and 5345 $\mu\text{g}/\text{mL}$, respectively, after the first dose. The mean $AUC_{0-2\text{wk}}$ (area under the serum drug concentration-time curve from 0 to 2 weeks post-dose) and mean C_{max} for male and female monkeys in the 30 mg/kg IV group were 301500 $\mu\text{g}\cdot\text{hr}/\text{mL}$ and 1510 $\mu\text{g}/\text{mL}$, respectively, after the 13th dose (i.e., steady state). The

AUCs were used to calculate the safety margins for the dose levels planned for this Phase 2 study. Refer to Section 8.1.3.1 for additional details on safety margins and selection of doses.

4.3.3 Clinical Program

The clinical program comprises a Phase 1a/1b study (4083-001, completed in December 2014) in subjects with mild to moderate plaque-type psoriasis at 4 clinical sites in Canada. KHK4083 was well-tolerated and no dose-limiting toxicity was identified in the Phase 1a/1b, single-ascending dose study of up to 10 mg/kg, the highest dose studied.

The implementation of this study is based on the premise that KHK4083 may have the potential to reduce OX40-bearing lymphocytes, which have been reported in colonic biopsies of patients with UC. (Stüber, 2000) In sites of mucosal inflammation, the expression of OX40 ligand on gut endothelial and OX40+ cells was increased in the colon and jejunum of patients with IBD. (Souza, 1999) Thus, further study of KHK4083 is planned for IBD, in particular in subjects with UC.

5 OBJECTIVES

The primary, secondary (including PK and immunogenicity), and exploratory objectives of the study (refer to Appendix 1 for primary and secondary efficacy definitions) are as follows:

Primary:

- **Induction Therapy - Part A:** To determine the safety and tolerability of administration of multiple ascending doses of KHK4083 and to select the highest dose tolerated by subjects with moderately active UC to recommend for use in Part B;
- **Induction Therapy - Part B:** To determine if the recommended dose of KHK4083 identified in Part A improves the mucosa in subjects with moderately active UC at Week 12 as measured by the modified Mayo endoscopy subscore (mMES).

The assessment is based on a mean change in the mMES (subscores from 0 to 3 with modified endoscopy finding scoring, i.e., excluding mild friability from a subscore of 1) from Baseline (Week 0) to Week 12. Refer to Mayo Clinic Scoring System for Assessment of Ulcerative Colitis Activity (Score 0 to 12) with Modified Mayo Endoscopy Subscore Appendix 2 for the mMES Scoring System.

Secondary:

- To determine if KHK4083 at dose levels different than the recommended dose improve the mucosa based on the mMES;
- To determine if any dose level of KHK4083 administered as Induction Therapy will meet the following objectives at Week 12 (or as noted):

- Improve the mucosa based on the modified Baron endoscopic score; Refer to Appendix 3 for the modified Baron scoring system.
 - Improve the mucosa based on the Ulcerative Colitis Endoscopic Index of Severity (UCEIS);
The assessment is based on a mean change in the UCEIS (scores from 0 to 8, based on findings of vascular pattern, bleeding, and erosions/ulcers) from Baseline (Week 0) to Week 12. Refer to Appendix 4 for the UCEIS Scoring System.
 - Induce mucosal healing based on the mMES;
 - Improve clinical signs and symptoms based on total Mayo Clinic score;
 - Improve clinical signs and symptoms based on partial Mayo Clinic scores (Week 2 through Week 12, excludes endoscopy subscores);
 - Induce a clinical response based on a reduction in the total Mayo Clinic score (i.e., reduction of at least 3 points and a decrease of at least 30% from Baseline [Week 0] to Week 12) and rectal bleeding subscale (i.e., reduction of at least 1 point from Baseline [Week 0] to Week 12) (or a defined absolute rectal bleeding score of 0 or 1 at Week 12);
 - Induce clinical remission based on a total Mayo Clinic score (i.e., score of ≤ 2) and subscores (i.e., no subscores > 1).
 - To characterize the PK of KHK4083 in subjects with moderately active UC following multiple dose administration;
 - To evaluate the development of antibodies against KHK4083 (immunogenicity).
- Refer to Section 10.2 for additional details on all secondary endpoints.

Exploratory:

- To determine if multiple doses of KHK4083 administered during the Open-label Extension (OLE) / Long-term Extension (LTE) Therapy phase will meet the following objectives at Week 52 (or as noted) when compared with Baseline (Week 0) scores (or subscores) or assessments:
 - Improve clinical signs and symptoms based on total Mayo Clinic score;
 - Improve clinical signs and symptoms based on partial Mayo Clinic scores (excludes endoscopy subscores) at Week 16 through Week 52, and the LTE Therapy Follow-up Period (Week 56 through Week 64);
 - Induce a clinical response based on a reduction in the total Mayo Clinic score and rectal bleeding subscale (or a defined absolute rectal bleeding score);
 - Induce clinical remission based on a total Mayo Clinic score and subscores;
 - Induce durable clinical responses and durable clinical remissions (present at both Weeks 12 and 52), and glucocorticoid-free clinical remission;
 - Induce mucosal healing based on the mMES;
 - Improve the mucosa based on the mMES, UCEIS, and/or modified Baron endoscopic score;

- Induce remission (Week 12; Week 52) based on modified Mayo endoscopy, stool frequency, and rectal bleeding subscores (defined as an mMES of 0 or 1, stool frequency subscore of 0 or 1, and rectal bleeding subscore of 0);
- To evaluate the activity of KHK4083 on health-related quality of life (HRQL), which will be based on the subject's completed Inflammatory Bowel Disease Questionnaires (IBDQs) in comparison to Baseline assessments;
- To measure changes from Baseline in corticosteroid (glucocorticoid) dosages;
- To determine the percentage of subjects who are glucocorticoid-free from Week 16 through Week 52, and through the OLE/LTE Therapy Follow-up Period (Week 56 through Week 64);
- To evaluate the pharmacodynamic (PD) profile of KHK4083;
- To explore the PK-PD relationships.

Refer to Section 10.3 for additional details on exploratory endpoints.

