 - c) tumor necrosis factor-alpha antagonists for induction therapy with approved anti-TNF products including, but not limited to, infliximab 5 mg/kg IV for 2 doses at least 2 weeks apart, adalimumab 160 mg SC followed by at least 80 mg SC at least 2 weeks apart, and golimumab 200 mg SC followed by at least 100 mg at least 2 weeks apart and anti-TNF biosimilar products with approved dosages for 2 doses at least 2 weeks apart; or as maintenance therapy for recurrence of symptoms despite continued dosing, or history of intolerance

(including but not limited to infusion or injection reactions, demyelination or infection).

- 7) Female subjects who are considered to be women of childbearing potential (WOCBP) must have a negative pregnancy test at Screening and Baseline. WOCBP must agree to use effective contraception, defined as oral contraceptives with one barrier method, or tubal ligation with one barrier method or double barrier method (condom plus spermicide or diaphragm plus spermicide) during the study and for at least 6 months after the last dose of investigational product. Subjects are considered to not be of childbearing potential if they are ≥ 50 years of age and without menses for 24 consecutive months and have a follicle-stimulating hormone (FSH) level > 25 mIU/mL (or in postmenopausal range per local laboratory standards); or have undergone a hysterectomy and/or a bilateral salpingo-oophorectomy.
Egg donation is not permitted while on study medication and for at least 6 months after the last dose of study medication.
- 8) Male subjects (including those who have had a vasectomy) must use adequate contraception (e.g., latex condom, non-latex condom not made of natural animal membrane such as polyurethane condom) during the study and for at least 6 months after the last dose of investigational product.
Sperm donation is not permitted while on study medication and for at least 6 months after the last dose of study medication.

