8.5 Prior and Concurrent Therapy

All medications (including prescription, non-prescription and supplements) for treatment of UC taken within 6 months prior to Screening; any other medication taken 1 month prior to Screening; and any concomitant medications (including tracking probiotic usage) during the study will be collected. For all biologic treatments, the reason for discontinuation should be collected at Screening. Combination medications should be recorded by trade name.

Stable doses of the following concomitant medications are permitted for UC treatment during the study as specified below:

- Aminosalicylates (5-ASA or mesalamine ≤ 4.8 g/day; sulfasalazine ≤ 3 g/day) for at least 14 days prior to the Screening visit; and/or
- Oral glucocorticoids, ≤ 20 mg/day prednisolone or the equivalent, or budesonide ≤ 9 mg/d for at least 14 days prior to the Screening visit (or for 4 weeks if a course of corticosteroids had started at less than 8 weeks prior to Screening visit); and/or
- Azathioprine up to 3 mg/kg/day or 6-mercaptopurine up to 1.5 mg/kg/day for a total treatment period of at least 12 weeks, including 4 weeks of stable treatment, prior to the Screening visit.

Supportive therapy to manage symptoms or AEs is acceptable. Daily, chronic antidiarrheals should not be taken.

One bolus or “rescue” treatment for up to 7 days with each of the following: systemic corticosteroids or topical corticosteroid enemas or suppositories (in addition to the dose of oral corticosteroids at Screening) is permitted only after Week 12 evaluations are complete. Topical anti-inflammatory agents may be permitted only after Week 12 evaluations are complete and application must be withheld for at least 2 weeks prior to the sigmoidoscopy at Week 52/End-of-Treatment visit.

Dose reductions of concurrent medications are permitted for AEs from Baseline through the end of the study as allowed by the protocol. Other dose adjustments of concurrent medications (including corticosteroids and other treatments for UC) are permitted after the Week 12 visit (per Investigator’s judgment), i.e., during OLE/LTE Therapy and the Induction Therapy and OLE/LTE Therapy Follow-up Periods. After the Week 12 visit, corticosteroid (glucocorticoid) dosages of prednisolone or its equivalent may be tapered by approximately 2.5 mg/day per week, at the Investigator’s discretion. Subjects who have recurrence of clinical symptoms may increase their chronic (> 7 days) dose of corticosteroids and other

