8.5.1 Prohibited Treatment

During Screening and Induction Therapy, subjects are not permitted to receive rescue therapy for UC including increases in corticosteroids or other medications for UC treatment, except as specified above (Section 8.5).

During Screening, Induction Therapy, and OLE/LTE Therapy, subjects are not permitted to receive any additional experimental therapy or any other therapy to treat the UC, except as specified above. The following is a list of specific prohibited treatments:

- B-cell depleting agents including vedolizumab, natalizumab, efalizumab or rituximab or other lymphocyte-depleting treatments, including but not limited to alkylating agents (such as cyclophosphamide or chlorambucil) and total lymphoid irradiation;
- Methotrexate, cyclosporine, mycophenolate, tacrolimus, thalidomide, or other immune altering drugs; (*Note: ophthalmologic preparations are permitted.*)
- TNF antagonists.

The above prohibited treatments are permitted during the Induction Therapy Follow-up Period and OLE/LTE Therapy Follow-up Period of the study.

Some medications, such as nonsteroidal anti-inflammatory drugs, may need to be administered or held prior to a sigmoidoscopy with biopsy. Those will be detailed in a sigmoidoscopy manual.

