4.4 Handling of missing and incomplete data

Available data at each time point will be presented. The denominator for percentages will be based on the number of subjects in the appropriate treatment or cohort group for summary purposes.

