7.3 Analysis of exploratory efficacy endpoints

All exploratory efficacy variables will be summarized by treatments. The changes from Baseline in mMES, UCEIS and total Mayo Clinic score as well as Baseline and Week 52 will be summarized by treatments. In addition, the partial Mayo Clinic scores (without sigmoidoscopy) and changes from Baseline will be summarized by study visit at Weeks 16, 20, 24, 28, 32, 36, 40, 44, 48, and 52 and at OLE/LTE Therapy Follow-up Period visits (Weeks 56, 60, and 64).

The change from Baseline in HRQL based on IBDQ will be analyzed for total score and 4 subscale scores at all study visits (Weeks 2 to 52, including Induction Therapy Follow-up Period visits (Weeks 16, 20, and 26) and OLE/LTE Therapy Follow-up Period visits (Weeks 56, 60, and 64).

Remission (mMES of 0 or 1, stool frequency subscore of 0 or 1 and rectal bleeding subscore of 0) rates at Week 12 will be summarized. Remission rates at Week 52 will be summarized by Double-Blind Period and OLE Therapy Period as well.

Clinical response and clinical remission will be summarized at Week 52. The percentage of subjects with mucosal healing, and the percentages of subjects with improvement in the mucosa (change from Baseline of at least a 1-point improvement in the mMES and/or in the modified Baron endoscopic scores) at Week 52 will be summarized by Double-Blind Period and OLE Therapy Period.

Durable clinical response and durable clinical remission at Week 52 will be summarized by Double-Blind Period and OLE Therapy Period. Durable clinical response and durable clinical remission at Week 52 will be defined as follows:

- Duration clinical response at Week 52 will be defined in the case that clinical response is present at both Weeks 12 and 52.
- Duration clinical remission at Week 52 will be defined in the case that clinical remission is present at both Weeks 12 and 52.

Glucocorticoid-free clinical remission at Week 52 will be summarized by Double-Blind Period and OLE Therapy Period. At Weeks 16 through 52 and through the OLE/LTE Therapy Follow-up Period (Week 56 through Week 64), the change from baseline in corticosteroid (glucocorticoid) dosages and the duration of glucocorticoid-free treatment will be summarized. Those parameters definitions are shown below.

- Glucocorticoid-free clinical remission at Week 52

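### Follow-up partial Mayo and IBDQ scores are summarised by KHK4083 treatment with no rule for scores taken after other, newly permitted UC drugs are started

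*Protocol*

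**What the plan says.** **Objective.** Protocol Section 5 (Exploratory) opens with "To determine if multiple doses of KHK4083 administered during the Open-label Extension (OLE) / Long-term Extension (LTE) Therapy phase" and asks for improvement against Baseline. For partial Mayo this runs "at Week 16 through Week 52, and the LTE Therapy Follow-up Period (Week 56 through Week 64"). Section 10.3 turns it into an endpoint for subjects who received both induction and OLE/LTE therapy.

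**Permitted drugs.** Protocol 8.5.1 introduces its bans with "The following is a list of specific prohibited treatments". The list covers vedolizumab and lymphocyte-depleting agents; methotrexate, cyclosporine, mycophenolate, tacrolimus and other immune-altering drugs; and TNF antagonists. The section then says: "The above prohibited treatments are permitted during the Induction Therapy Follow-up Period and OLE/LTE Therapy Follow-up Period of the study".

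**Summaries.** SAP 7.3 summarises partial Mayo and its change from Baseline by treatment, including "at OLE/LTE Therapy Follow-up Period visits (Weeks 56, 60, and 64"). It analyses IBDQ at Weeks 16, 20 and 26 after induction only, and at Weeks 56, 60 and 64.

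**Model.** SAP 7.3 also fits an MMRM to change in partial Mayo over the Double-Blind Therapy Period and its follow-up. It reports dose-versus-placebo differences with confidence intervals and p-values at each visit. Note 2 to Table 2 in SAP 4.1 defines the double-blind follow-up as covering follow-up after both the double-blind and the LTE periods. Protocol 8.1.5 puts the induction-only follow-up visits at Weeks 16, 20 and 26.

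**Data rule.** SAP 4.4 says: "Available data at each time point will be presented".

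**The concern.** The follow-up values answer a question about KHK4083, yet they are taken when effective competing drugs may be in use. A subject who relapses, or who never responded, is a natural candidate for another agent. Any improvement that follows would sit in that subject's KHK4083 row with nothing to mark it.

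At stake is how the off-treatment course is read. A follow-up mean that looks sustained could be partly the work of a TNF antagonist. SAP Section 1 says its planned analyses will go into regulatory submissions or manuscripts, so an unlabelled mean can travel beyond the study report.

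**Working it through.** **1. Is there a rule anywhere that handles such scores?**
- Protocol 12.6 leaves missing values missing and says nothing about scores after other therapy.
- Protocol 12.7 allows exclusions after a protocol violation. Use permitted by 8.5.1 is not a violation.
- SAP 7.3 and 9.3 derive glucocorticoid variables, limited to ATC code H02AB. TNF antagonists and vedolizumab fall outside that definition.
- SAP 5.5 tabulates concomitant medications by period without linking them to scores.

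None of these excludes, flags or tests sensitivity to the affected scores.

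**2. Timing.** The last dose is at Week 10 (induction only) or Week 48 (OLE/LTE). Simulated half-lives run from 10.5 days (1.0 mg/kg) to 26.2 days (10 mg/kg) in Protocol Table 8.1.3-1. Half-lives elapsed = days since last dose / half-life.
- Week 16: (16 - 10) x 7 = 42 days; 42/26.2 = 1.6 to 42/10.5 = 4.0 half-lives.
- Week 56: (56 - 48) x 7 = 56 days; 2.1 to 5.3 half-lives.
- Weeks 26 and 64: 16 x 7 = 112 days; 4.3 to 10.7 half-lives.

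KHK4083 exposure is therefore falling while the other drugs are allowed. Inclusion 6c accepts "infliximab 5 mg/kg IV for 2 doses at least 2 weeks apart" as an induction course. Two such doses fit within Weeks 12-26 (14 weeks) or Weeks 52-64 (12 weeks).

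**3. Within-arm shift.** The plan states no figure on this point. Let f be the share of an arm that starts another drug and d the change in partial Mayo that the drug causes. Neither is in the documents. The shift in the arm mean is f x d.
- f = 0.1, d = -1: -0.1 points.
- f = 0.3, d = -2: -0.6 points.
- f = 0.5, d = -3: -1.5 points.

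In a 9-subject Part A dose group, one starter improving by an assumed 3 points moves the mean by 3/9 = 0.33.

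**4. Dose-versus-placebo shift.** This is (fK - fP) x d, where fK and fP are the shares starting on KHK4083 and on placebo. With assumed d = -2:
- 30% vs 10%: 0.2 x -2 = -0.4 (favours KHK4083).
- 20% vs 20%: 0.
- 10% vs 30%: -0.2 x -2 = +0.4 (against KHK4083).

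**5. Which handling helps?** Assume 70% hold a change of -4, and 30% relapse to 0 and then start a drug worth -2.
- Without the other drug: 0.7 x -4 + 0.3 x 0 = -2.8.
- All data: 0.7 x -4 + 0.3 x -2 = -3.4, overstated by 0.6.
- Values before the start only: -4.0, overstated by 1.2.
- Last value before the start carried forward: -2.8 if that value already shows the relapse; -4.0 if it was recorded before the relapse.

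Dropping starters does worse than all data whenever the other drug fails to bring relapsers back to the level of non-starters.

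**The case against.** The best defence is that these are exploratory summaries, that using all observed data is a legitimate choice, and that subject-level medication and Mayo listings (SAP Listings 16.2.5-1 and 16.2.6-2.2) let a careful reader find the affected values. Each part is true. But the reader would have to rebuild the summary by hand, and Tables 14.1-3.3 and 14.1-3.4 pool extension and follow-up medications.

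Several stronger readings are tempting, and the documents do not support them:
- **That follow-up improvement is always credited to KHK4083.** This direction is clear only for within-arm change, and only if the other drug helps. Placebo subjects may start other drugs too, so the MMRM contrast can move either way.
- **That the stated objective covers Weeks 16-26.** It names Weeks 56-64. Partial Mayo at Weeks 16-26 enters through the SAP's follow-up definition and the MMRM.
- **That follow-up means are the plan's durability measure.** Durable response and remission are defined at Weeks 12 and 52 (Protocol 10.3), and Protocol 9.4 describes the follow-up as a safety period.
- **That Inclusion 6c shows scores would fall in the window.** It defines prior unsuccessful therapy. It shows only that two doses fit.
- **That Weeks 16-26 are full of switchers.** Amendment 1 sent subjects without clinical response or mucosal healing to that follow-up. Amendment 2 opens the OLE to induction completers regardless of response. The documents give no count.

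One limit stands. Protocol 8.5 also allows dose adjustments of existing UC medication "during OLE/LTE Therapy and the Induction Therapy and OLE/LTE Therapy Follow-up Periods". A flag built on the 8.5.1 list will not capture those.

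**Conclusion.** The gap is real and of modest weight. The plan permits other UC drugs in follow-up, reports follow-up efficacy by KHK4083 treatment, and does not separate the two. Within-arm follow-up change from Baseline would overstate benefit if the other drug helps. The OLE follow-up is the clearest case, since by then placebo-randomised subjects have also received KHK4083 and no untreated comparator remains. For the MMRM the direction is unknown.

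The size cannot be derived from the documents. The 0.1 to 1.5 point range rests wholly on assumed values of f (10-50%) and d (1-3 points). A reader might carry the doubt over to the main result, but the primary endpoint and the proof-of-concept decision (SAP 4.5) use 12-week induction data and are untouched. The change is worth making because it is cheap and the follow-up rows cannot be interpreted without it.

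**What to change.** In SAP 7.3, and in the follow-up partial Mayo and IBDQ tables and figures:
- Derive a flag, from concomitant-medication dates, for every value on or after the start of a treatment listed in Protocol 8.5.1. State a rule for partial start dates, and note that adjustments under Protocol 8.5 are not covered.
- Show the number of starters by arm and visit.
- Keep the all-data summary. Beside it, add a sensitivity summary in which flagged values are replaced by the last value before the start. Do not make the pre-start subset the main result, because it removes relapsers and can inflate the mean further. Say in a footnote that carrying forward is also optimistic when the last value predates the relapse.
- For the MMRM, add a sensitivity run that excludes flagged values or ends at each subject's last on-treatment visit, and label the follow-up visits as off-treatment data.

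Cost: SAP wording, one derived flag and a few extra rows. Medication dates are already collected through follow-up (Protocol 8.5; SAP 5.5). No visit or procedure is added, and which treatments are permitted does not change.
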